6.1 Treatment groups

Patients will be assigned to one of the following groups:

- Active taVNS
- Sham stimulation

6.2 Treatment dosing

taVNS will be delivered to the left ear only in one configuration: active (tragus) using a Digitimer Type DS7AH (Digitimer Ltd, Hertfordshire, England) TENS unit cleared by the FDA for electrical nerve stimulation. A clip electrode will be used to stimulate at one of the two positions.

Stimulation will be delivered at a constant current (200% perceptual threshold). Perceptual threshold is defined by the minimum amount of current perceived by the participant. This ranges between 0.5mA to 1.5mA depending on individual anatomical differences. Each taVNS treatment visit will be identical: 1 hour of taVNS (duty cycle: 1min on, 30 sec off)

6.3 Management and reporting adverse events

Management: All adverse events occurring after randomization and during the treatment period, regardless of adherence to study treatment, will be recorded at all visit contacts. Procedures will be promptly discontinued if the participant reports significant distress that does not improve with time or intractable side effect of taVNS.

Importantly, all of these methods have been done before, and published by our and other groups in adults, and we believe these extra precautions will assure the safety and well-being of any participants enrolled.

Patients and caregivers will be asked about visits to doctors, healthcare providers, and emergency departments for other than routine care. The Principal Investigator (PI) will be responsible for monitoring the safety of patients, as well as for appropriate medical care of patients during the study in connection with study procedures.

Safety assessments will include physical exam, vital signs (heart rate primary measure, with additional blood pressure, respiratory rate and pulse oximetry monitoring), MDS UPDRS examinations and Cognitive examinations, Columbia- Suicide Severity Rating Scale

(C-SSRS), monitoring of adverse events, and monitoring and maintenance of concurrent medication records.

Reporting:

The supervising Institutional Review Board (IRB) will be notified of adverse events, risks, or unanticipated problems according to their reporting requirements. If any adverse events are noticed which are not described in the consent or are serious, we will inform the IRB before continuing with the next enrolled subject. Data collected regarding serious adverse events will include the treatment provided, outcome, and presumed relationship to study stimulation and will be updated as new information becomes available; a narrative description also will be provided.

Data Safety Monitoring Board will be utilized. See full description below; An independent review committee charged to monitor the conduct of the protocol to ensure the safety of participants and the validity and integrity of the data.

7. Screening and Baseline visit

7.1 Overview

Obtain Informed Consent, as outlined below. Review inclusion and exclusion criteria, medical history, demographics. We will obtain a baseline MoCA exam, based on proposed exclusionary criteria. For those enrolled, medications used in the treatment of PD will be held constant throughout the study. Baseline blood draw for biomarkers will be obtained. We will randomize the patient to sham (n=15) versus active taVNS stimulation (n=15), and obtain baseline cognition battery (in normal *ON PD medication state*) at this time. Cognitive battery outlined below.

7.2 Overview of consent issues

Informed consent will be obtained from the participant prior to the initiation of any study related procedures. Either the study coordinator or the physician investigator will obtain the consent. The informed consent session will be conducted and documented according to local IRB requirements, as outlined in consent procedure section below

7.3 Review Medical History

The principal investigator or designated study physician must see the patient before randomization. The physician is responsible for fully assessing whether the patient has any of the conditions listed as contraindications, chiefly a history of myocardial infarction or

arrhythmia, bradycardia, epilepsy, metal implants above the shoulders, active respiratory disorder. The presence of any contraindicated condition or medication, which are itemized in the baseline eligibility, constitutes an exclusion criterion.

8. Stimulation Visits

At **visit 1**, MDS UPDRS motor evaluation will be videotaped in the *OFF PD medication state* (defined as at least 12 hours without PD medication).

Stimulation dosing will be assessed as above. Then taVNS or sham stimulation will occur over 1 hour. Acute pupillometry testing will be done. Then repeat MDS UPDRS motor evaluation will be videotaped (assessment of acute taVNS effect). A blinded rater will later score the modified (minus rigidity) MDS UPDRS on all videos at completion of the study.

Visits 2-4 are routine stimulation treatment visits in the *ON med state* with safety assessments, but no efficacy measures.

Visit 5 (study mid point) includes *OFF med* motor evaluation pre/post stimulation as at visit 1, in addition to the stimulation session. (used as mid point motor evaluation).

Visit 6 is a stimulation treatment visits in the *ON med* state with additional behavioral saccade testing. (used as mid point cognition marker free of practice effects, not administered at visit 5, as visit 5 is an *OFF med* visit)

Visits 7-8 are taVNS treatment visits in the *ON med state* with safety assessments, but no efficacy measures.

Visit 9 is an *ON med* stimulation visit, and includes repeat cognition battery following the stimulation session. (The cognition battery is not administered at visit 10, as visit 10 is an *OFF med* day.)

Visit 10 (final day of stimulation) includes *OFF med* motor evaluation pre/post stimulation as at visit 1, in addition to the stimulation session. Repeat blood draw.

9. Specimen Collection

Consented patient participants will be assigned a random *4-digit study ID number and blood serum samples will be drawn by appropriately trained staff. There will be two blood draws per patient; one baseline and one at the conclusion of the study. Blood samples will be delivered to [name] lab as soon as possible, following all standard procedures for safe transportation and storage. [name] personnel will be blinded to sample name, diagnosis, and all other personal identifiers.

A paper log containing names and corresponding study IDs will be kept in a locked room and locked filing cabinet in the Movement Disorder Program Suite. This room will not be accessed by patients, and is separate from the room where patient evaluations are performed.

10. Follow up visit

Visit 11 (Safety follow up visit) 6-14 days after visit 10, we will check for any adverse events that might have occurred since the last stimulation session, just as we have with every visit.

11. Outcomes Assessments

11.1 Primary outcome: Clinically meaningful treatment difference of the MDS - UPDRS motor section

Videotaped, modified UPDRS evaluations have been established as a reliable research method with very high correlation to full UPDRS assessments.¹⁴ The UPDRS is modified due to the fact rigidity is not assessed by a rater watching a videotaped examination.

The six motor examinations will be compared for both acute as well as cumulative effects of stimulation:

- 1) Visit 1 pre-stimulation comparison to visit 1 post stimulation: acute effect
- 2) Visit 5 pre-stimulation comparison to visit 5 post stimulation: acute effect
- 3) Final Visit 10 pre-stimulation comparison to Visit 10 post stimulation: acute effect
- 4) Visit 5 pre stimulation comparison to Visit 10 pre-stimulation: subacute effect
- 5) Visit 1 pre-stimulation comparison to final Visit 10 pre-stimulation: subacute effect
- 6) Visit 1 pre-stimulation comparison to final Visit 10 post-stimulation: subacute effect

11.2 Secondary outcomes: Cognition and Biomarkers

To examine taVNS effect on cognition, a battery of behavioral and cognitive tasks relevant to PD will be assessed. We will utilize both objective and subjective measures. We will assess baseline, midpoint, and final cognitive function.

Cognitive battery:

- 1) DKEFS (Delis-Kaplan Executive Function System) verbal fluency and switching:
10 minutes
- 2) Stroop written test: 4 minutes (including start up and instructions)
- 3) Digit symbol computer based: 4 minutes (including start up and instructions)
- 4) Digit span forward and backwards: 3 minutes
- 5) Fixation (control), Reflexive, and saccade inhibition tasks: 5 minutes (including start up and instructions)

Additional subjective patient reported measures:

- 1) CAARS (Conners' Adult ADHD Rating Scales) (3 minutes)
- 2) PROMIS Sleep-Related Impairment (1 minute), PROMIS Applied Cognitive Abilities (1 minute), PROMIS Fatigue (1 minute)

To examine taVNS effect on serum markers associated with PD and neurobiology of VNS, measures of BDNF, TNF-alpha, and IL-6 will be obtained at baseline and after completion of final stimulation session. Laboratory samples will be assayed using ELISA.

To examine whether taVNS leads to the predicted pupillary resting state dilation, Eye tracking with computerized software will be used.

Pupillometry will involve a computer-based system in which an individual will receive stimulation while software records the movements and dilation of the pupil. The system used involves a setup in which infrared cameras are used to monitor the pupil in a luminance-controlled room. Participants will look at a computer screen and be instructed to maintain gaze within a specific area of the screen. IR cameras will track and monitor pupil diameter during stimulation.

11.3 **Tertiary outcome:** Safety and Tolerability

Safety and tolerability will be monitored for mean change, at each visit, from baseline to follow up. All stimulation visits include monitoring adverse events as well as vital signs. 3 visits include C=SSRS admin, 2 visits include cognition battery, 2 visits include additional physician physical examination. The follow up visit will be one additional visit 6-14 days following stimulation to specifically monitor for delayed adverse events, and will include a physical examination. Adverse events will be documented.

12. Statistical Analysis

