VNS and PD: VNS is FDA approved for treatment-resistant epilepsy and depression. The vagus nerve does not have direct connections to cortical regions but rather sends projections through brainstem nuclei, which then relay signals to upper cortical regions. One of these brainstem nuclei used as a relay site is the locus coeruleus (LC), which contains noradrenergic (NA) neurons.¹ VNS increases NA concentrations in the prefrontal cortex of rats, NA neuronal firing rate in LC,² as well as brain derived neurotrophic factor (BDNF) expression in the cortex and hippocampus.³ The loss of LC-NA neurons is significant in PD⁴ and occurs earlier in the disease process than the loss of substantia nigra dopamine (SN-DA) neurons.^{5,6} Additionally, SN-DA neurons become more sensitive to various insults in the absence of NA nerve fibers.^{7,8} NA depletion itself has been implicated in a multitude of pathophysiologic mechanisms in PD, and includes gait dysfunction, dysautonomia, depression, apathy, inattention, and sleep disturbance.⁹

Preliminary data from our neuroscience laboratory (PI-[name]) shows that stimulating the vagus nerve for two weeks improved motor function and resulted in neurorestorative effects on DAergic and NAergic systems, and reduced cellular expression of alpha-synuclein¹⁰ in DA/NA double-lesioned rats. In addition, VNS resulted in a significant increase in BDNF levels in the target regions of the DA and NA neurons. VNS has also been shown to produce an anti-inflammatory effect by decreasing pro-inflammatory cytokines, increasing anti-inflammatory cytokines, and reducing gliosis in models of PD.¹⁰ These results provide pre-clinical evidence for VNS as a potential treatment strategy for PD patients; potentially addressing neuronal damage as well as motor and non-motor symptoms of the damaged noradrenergic and dopaminergic pathways.

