Specific Aim 1: To examine in a 2-week, randomized, sham controlled, double blind trial the effect of taVNS on motor symptoms in patients with mild to moderate motor symptoms of PD.

Hypothesis: taVNS will be superior to sham stimulation on its effects on the motor section of the Movement Disorder Society Unified Parkinson's Disease Rating Scale (MDS UPDRS; primary outcome measure).

Specific Aim 2: To examine in a 2-week, randomized, sham controlled, double blind trial the effect of taVNS on cognitive symptoms in PD.

Hypothesis: taVNS will be superior to sham stimulation on its effects on a composite score of the following cognitive assessment tools: DKEFS, Stroop, Digit symbol, Digit span forward and backwards, Fixation (control), Reflexive, and saccade inhibition tasks, CAARS, PROMIS (secondary outcome measure).

Specific Aim 3: To assess safety and tolerability of taVNS in PD.

Hypothesis: Treatment with taVNS will be as well tolerated as sham stimulation on the following parameters: acute monitoring of vital signs, MDS UPDRS motor evaluations and cognition testing to evaluate for worsening PD severity, adverse events or serious adverse events assessments, and the Columbia Suicide Severity Rating Scale (CSSRS). (tertiary outcome measure)

Specific Aim 4:(exploratory aim) To evaluate effects of taVNS versus sham stimulation on biomarkers relevant to VNS neurobiology.

Hypothesis: taVNS and not sham stimulation will lead to a decrease in serum inflammatory biomarkers (TNF-alpha, and IL-6), increase in serum BDNF, and increase in resting pupil diameter.

3. Design

Overview:

This pilot study of taVNS in PD intends to prove basic concepts of acute motor and cognition improvements with taVNS in PD patients. We will accomplish this by a two-week, single site, parallel, randomized, double blinded, sham-controlled pilot study of taVNS in 35 PD patients. There will be 1 screening visit, 10 stimulation visits, and 1 follow up visit.

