taVNS vs sham stimulation		x	x	x	x	x	x	x	
pupillometry		x							
saccade					x				
Vital Signs		x	x	x	x	x	x	x	
Post-stim MDS UPDRS		x		x				x	
Monitoring AE		x	x	x	x	x	x	x	x

MDS-UPDRS- Movement Disorder Society- Unified Parkinson's Disease Rating Scale (motor portion used)

C-SSRS- Columbia-Suicide Severity Rating Scale

[figure not shown]
taVNS- transauricular vagal nerve stimulation

saccade- Fixation (control), Reflexive, and saccade inhibition tasks. This is INCLUDED in cognitive battery, but will be done as a stand-alone test on stim day 6

Cognitive Battery- DKEFS, Stroop test, Digit-Symbol test, Digit Span, saccade,

Patient reported measures- CAARS, PROMIS (fatigue, sleep related, Applied Cognitive Abilities)

Figure 1: Overview of Study Flow / Assessments

4. Eligibility Criteria

Inclusion Criteria:

Age: 40-82 y
Idiopathic Parkinson's Disease Diagnosis
Disease Stage: Hoehn and Yahr stage 2-3
Patient requires a minimum of 3 doses of levodopa daily
Willingness to be videotaped

Exclusion criteria:

Dementia or MoCa <24
PD psychosis
Ear trauma
Facial pain
TBI or clinical history of stroke
Metal implants above the shoulders
History of myocardial infarction or arrhythmia, bradycardia
Active respiratory disorder
Alcohol or substance use disorders
History of DBS or other brain surgery
Epilepsy
Pregnancy
B-Blockers, dopamine blocking agent, antiarrhythmic medication, acetylcholine esterase inhibitor, midodrine, florinef, droxidopa, or anticholinergic drugs

5. Randomization and masking

Randomization of the 35 subjects will be designed to yield an expected assignment ratio of 1:1 for taVNS and sham stimulation. Treatment assignments will be masked to the patients and to all study personnel with exception of PI and others vital to providing the actual treatment. Patients will be masked to transcutaneous stimulation of the auricular branch of the vagus nerve at the tragus, versus sham stimulation. Sham stimulation involves identical perceptual threshold finding and stimulation parameters as active stimulation, with the exception of stimulation target. Sham stimulation will be delivered to the left earlobe, a target

believed to have little to no vagal nerve innervation. A blinded MUSC Movement Disorder Neurologist will rate six videotaped MDS UPDRS examinations. Rater will be blinded to sham versus active stimulation, pre-stimulation versus post-stimulation state, and to the stimulation day of study.

6. Treatment plan

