12.2 Secondary analysis: Cognition and Serum markers

Measures of central tendency and distribution characteristics will be examined for all measures. Appropriate transformations and screening of outliers will be applied as indicated.

Generalized eta-squared¹⁵ will be calculated from repeated measures ANOVAs to examine cognitive change between groups over the 2 time points. For each time point, a composite score for cognition will be estimated by the average of demographically-corrected raw scores. The subjective measures of cognitive functioning will be analyzed in a similar manner. Cohen's d will be used to examine effect of stimulation on serum biomarkers.

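### Aim 2 puts PROMIS Fatigue and PROMIS Sleep-Related Impairment into a composite labelled cognition, so its result can be shifted by non-cognitive change and a true cognitive effect diluted

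*Combined protocol and SAP*

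**What the plan says.** Section 2, Specific Aim 2, states the hypothesis that "taVNS will be superior to sham stimulation on its effects on a composite score of the following cognitive assessment tools". The list that follows ends with "saccade inhibition tasks, CAARS, PROMIS (secondary outcome measure"). PROMIS appears there as a whole, with no limit to one scale.

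The legend to the schedule of activities in section 3 says what PROMIS covers: "Patient reported measures- CAARS, PROMIS (fatigue, sleep related, Applied Cognitive Abilities"). That line stands apart from the line defining the cognitive battery.

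Section 11.2 presents objective and subjective measures as the way to examine the effect on cognition. It numbers five objective tests. Under the label "Additional subjective patient reported measures" it then lists CAARS and "PROMIS Sleep-Related Impairment (1 minute), PROMIS Applied Cognitive Abilities (1 minute), PROMIS Fatigue (1 minute").

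Section 12.2 forms the cognition composite as an average of raw scores corrected for demographics, without naming the components. It adds: "The subjective measures of cognitive functioning will be analyzed in a similar manner". The member scales are not named there either. The section gives no standardisation, alignment of direction, weights or success criterion for Aim 2.

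**The concern.** By their names, two of the three PROMIS scales measure tiredness and sleep, not cognition. Aim 2 lists PROMIS as a component, and no later section takes those two out or gives them an outcome or analysis of their own.

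The protocol's rationale makes this more than a formality. Section 1 attributes to noradrenaline depletion a range of problems that includes "depression, apathy, inattention, and sleep disturbance", and taVNS is meant to raise noradrenergic firing. An effect on sleep or fatigue without an effect on cognition is therefore plausible under the trial's own mechanism. It would enter the cognitive score and could not be told apart within it. Conversely, if taVNS helps cognition but not sleep or fatigue, the two unresponsive scales pull the average towards no effect. In a trial of 35 patients there is little precision to spare.

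**Working it through.** **The plan's own figure.** The only sample-size figure is 26 (13 per group) in section 12.3, for the motor outcome. With a difference of 3.25 − 1 = 2.25, SD 2.0, 80% power and two-sided 0.05, n per arm = 2 × (1.960 + 0.842)² × (2.0/2.25)² = 12.4, rounded up to 13. It reproduces with the normal approximation (the t version needs 13.4, so 14). No figure is given for cognition, so what follows rests on stated assumptions.

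**Inputs from the documents.** There are five numbered objective tests and four subjective scales (CAARS and three PROMIS scales) in section 11.2, so nine components if each counts once. Two of the nine, and two of the four subjective scales, are fatigue and sleep. With 35 patients at 1:1 the arms are 17 and 18 before any dropout.

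**Assumptions.** Each scale has SD 1, equal weight and the same direction of benefit. Every pair has correlation r, taken from 0.3 to 0.6. CAARS counts as cognition. Responding scales shift by 0.5 SD. Power is for a two-sample t-test at two-sided 0.05.

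**Formulas.** SD of the mean of k scales = √[(1 + (k − 1)r)/k]. Standardised effect = (share of scales that respond × 0.5) / that SD.

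| k | SD at r = 0.3 | SD at r = 0.6 |
|---|---|---|
| 2 | 0.806 | 0.894 |
| 4 | 0.689 | 0.837 |
| 7 | 0.632 | 0.811 |
| 9 | 0.615 | 0.803 |

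**Nine-component composite (Aim 2).**
- Dilution when only the seven other components respond: effect retained = (7/9) × SD₇/SD₉. At r = 0.3 this is 0.778 × 0.632/0.615 = 0.80. At r = 0.6 it is 0.778 × 0.811/0.803 = 0.785. The loss is 20% to 21.5%.
- Shift when only fatigue and sleep respond: (2/9) × 0.5 = 0.111. Then 0.111/0.615 = 0.18 and 0.111/0.803 = 0.14. Power at 17/18 is 8% to 7%.
- Sensitivity to the count, for r = 0.3 to 0.7: the loss is 25% to 28% with 7 components in all and 17% to 18% with 11.

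**Separate average of the four subjective scales (one reading of section 12.2).**
- Dilution when only CAARS and Applied Cognitive Abilities respond: effect retained = 0.5 × SD₂/SD₄. At r = 0.3 this is 0.5 × 0.806/0.689 = 0.585. At r = 0.6 it is 0.5 × 0.894/0.837 = 0.53. The loss is about 41% to 47%.
- As effect sizes, the four-scale average shows 0.25/0.689 = 0.36 to 0.25/0.837 = 0.30. The two cognitive scales alone show 0.5/0.806 = 0.62 to 0.5/0.894 = 0.56. Power at 17/18 is 18% to 14% against 43% to 36%.
- Shift when only fatigue and sleep respond by 0.5 SD: the same 0.36 to 0.30, with no cognitive effect present.

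**The case against.** The best defence is that the plan never says the two scales are averaged with the cognitive ones. The schedule legend and section 11.2 both set the patient-reported measures apart from the cognitive battery. Section 12.2 speaks of subjective measures of cognitive functioning, which can fairly be read as leaving out fatigue and sleep. Its reference to a similar manner may mean only that the same repeated measures ANOVA is run scale by scale, in which case nothing is averaged on the subjective side. Section 12.2 could even be read as limiting the main composite to the objective tests.

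All of this stands as far as section 12.2 goes: its text does not decide the matter, and the 40 to 47% figure applies under one reading only. None of it removes PROMIS from the composite in Aim 2. If section 12.2 was meant more narrowly, it conflicts with Aim 2. If it also leaves out fatigue and sleep, those two scales have no stated analysis.

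The arithmetic can also be challenged. Equal weights, unit SDs, aligned direction and a common correlation are not in the plan. With raw scores, each scale's influence depends on its spread, and scales running in opposite directions would partly cancel unless reversed. The power figures ignore the roughly 10% attrition expected in section 12.3. The sizes are therefore illustrations.

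**Conclusion.** The point holds for the composite as Aim 2 defines it: two scales that do not measure cognition are components of an endpoint labelled cognition, and section 12.2 leaves open whether they also enter a subjective average. Under the stated assumptions, a true cognitive effect loses about one fifth in a nine-component composite, or about 40 to 47% in a separate four-scale average. Actual weights are unknown.

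Two stronger readings are tempting and should be resisted. A reader might infer that better sleep or less tiredness alone could satisfy Aim 2. The documents set no success threshold for that aim: section 12.2 gives an effect size, and the 0.05 level is stated for the primary analysis and the power calculation. In the nine-component composite, a 0.5 SD gain in fatigue and sleep yields only d = 0.18 to 0.14, with power of 8% to 7%, barely above the 5% expected by chance. The result can be shifted; nothing shows that it would be met. A reader might also infer that any cognitive effect is cut by about half. That fits only the four-scale average, which is an interpretation of section 12.2 and not its text.

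This concerns a secondary outcome of a pilot study and leaves the primary analysis untouched. It is a cheap improvement.

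**What to change.** In Aim 2, section 11.2 and section 12.2:
- Remove PROMIS Fatigue and PROMIS Sleep-Related Impairment from every cognitive composite or average.
- Define subjective cognition as CAARS and PROMIS Applied Cognitive Abilities.
- Name the components of each composite, and say whether there is one or two.
- Report fatigue and sleep as separately named, non-cognitive patient-reported outcomes, each with a between-arm estimate and interval.

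Settle this before the cognitive data are examined by arm. It needs no new data, visits or patients. The only downside is two more exploratory lines in the report.

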At the **screening visit** (visit SC) we will obtain informed consent, review inclusion and exclusion criteria, medical history, demographics. We will obtain a baseline MoCA exam, based on proposed exclusionary criteria. For those enrolled, medications used in the treatment of PD will be held constant throughout the study. Baseline blood draw in the amount of 3 teaspoons (<15ML) for biomarkers will be obtained by appropriately trained personnel. Urine pregnancy test will be administered to women of childbearing potential. We will randomize the patient to sham (n=15) versus active taVNS stimulation (n=15), and obtain baseline cognition battery (in normal *ON PD medication state*) at this time.

At **visit 1**, MDS UPDRS motor evaluation will be videotaped in the *OFF PD medication state* (defined as at least 12 hours without PD medication). Stimulation or sham will occur over 1 hour as defined below, and then repeat MDS UPDRS motor evaluation will be videotaped. A blinded rater will later score the modified (minus rigidity) MDS UPDRS on all videos at completion of the study.

Visits 2-4 are stimulation treatment visits in the *ON med state* with safety assessments, but no efficacy measures.

Visit 5 (study mid point) includes *OFF med* motor evaluation pre/post stimulation as at visit 1, in addition to the stimulation session.

Visit 6 is a taVNS treatment visits in the *ON med* state with additional behavioral saccade testing.

Visits 7-8 are stimulation treatment visits in the *ON med state* with safety assessments, but no efficacy measures.

Visit 9 is an *ON med* stimulation visit, and includes repeat cognition battery following the stimulation session.

Visit 10 (final day of stimulation) includes *OFF med* motor evaluation pre/post stimulation as at visit 1, in addition to the stimulation session. Repeat blood draw.

Visit 11 (Safety follow up visit) six to fourteen days after visit 10, we will check for any adverse events that might have occurred since the last stimulation session.

SCHEDULE OF ACTIVITIES

	Screening Baseline			Maintenance Phase					Follow up
	Visit SC Week 0-2 (-14d)	Visit 1 Stim day 1	Visit 2-4	Visit 5	Visit 6	Visit 7-8	Visit 9	Visit 10	+6-14 days
Written Informed Consent	x								
Eligibility Criteria	x								
MoCA	x								
Med/Neuro History	x								
Physical Exam	x								x
Blood Draw	x								
Cognitive Battery	x						x		
C-SSRS	x				x		x		
Pre-stim MDS UPDRS		x		x					x
stimulation thresholds		x							

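### Section 12.2 plans only Cohen's d for the serum biomarkers: adjusting for the baseline sample would gain precision at no cost, and medication state at each draw should be recorded

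*Combined protocol and SAP*

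**What the plan says.** **Analysis.** For BDNF, TNF-alpha and IL-6, section 12.2 names Cohen's d as the measure of the stimulation effect. Its general paragraph allows transformations and outlier screening for all measures. It names no change score, covariate, test or confidence interval for the biomarkers. Aim 4 (section 2), labelled exploratory, compares taVNS with sham; section 11.2 lists the markers among the secondary outcomes.

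**Draws.** Section 11.2: "measures of BDNF, TNF-alpha, and IL-6 will be obtained at baseline and after completion of final stimulation session". Section 9 confirms two draws per patient. The first is at screening (section 3: "Baseline blood draw in the amount of 3 teaspoons (<15ML) for biomarkers will be obtained by appropriately trained personnel"; section 7.1: "Baseline blood draw for biomarkers will be obtained"). The schedule of activities heads that column "Visit SC Week 0-2 (-14d", so it can fall up to 14 days before visit 1. The second is at visit 10, which section 8 says "includes *OFF med* motor evaluation pre/post stimulation as at visit 1, in addition to the stimulation session. Repeat blood draw".

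**Medication state.** No state is given for either draw. At screening the staff "obtain baseline cognition battery (in normal *ON PD medication state*) at this time", and no medication hold is described. Section 8 keeps cognition testing away from OFF days: saccade testing is "not administered at visit 5, as visit 5 is an *OFF med* visit", and "The cognition battery is not administered at visit 10, as visit 10 is an *OFF med* day". The documents do not say whether PD medication is resumed at visit 10 before the blood is taken.

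**The concern.** With about 15 patients per arm, an unadjusted biomarker effect will be imprecise. The baseline sample is already being collected, and a plan that does not say how it will be used may lose information that costs nothing. It also leaves the form of the analysis to be settled later.

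The timing of the draws adds a smaller question. If screening blood is taken ON and visit 10 blood OFF, each patient's change contains a response to medication withdrawal as well as any effect of stimulation. Variation in that response between patients would widen the change score. Aim 4 is worded as an effect in the taVNS arm and not in the sham arm, which invites a reading within each arm. Such changes could not be attributed to stimulation.

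**Working it through.** **The plan's figures.** The documents give no SD, correlation, target effect or power for any biomarker. Their only power figure, 26 patients (13 per arm, section 12.3), is for the motor score. It reproduces: 2 × (1.960 + 0.842)² × (2.0/2.25)² = 12.4, rounded up to 13. It does not bear on the markers. With the 15 per arm of sections 3 and 7.1, a two-sided 5% t-test has 80% power at d = 1.06, and the 95% interval for d is about ±0.75 at d = 0.

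**Step 1: gain from baseline adjustment.** Assume variance 1 at each draw and baseline to visit 10 correlation r. The variance per patient is 1 for visit 10 level alone, 2(1 − r) for change, and 1 − r² after adjustment. The SE ratios are:

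| r | Adjusted vs change, √((1+r)/2) | Adjusted vs visit 10 level alone, √(1−r²) |
|---|---|---|
| 0.3 | √0.65 = 0.81 | √0.91 = 0.95 |
| 0.5 | √0.75 = 0.87 | √0.75 = 0.87 |
| 0.7 | √0.85 = 0.92 | √0.51 = 0.71 |

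At 15 per arm and r = 0.5, simulation gives 0.88 against a change score, slightly less gain than the formula.

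**Step 2: what unmatched draws could cost.** Suppose screening is ON and visit 10 OFF. A shift common to both arms cancels: simulated with a true difference of 0.80, the between-arm difference was 0.80 in every setting. Now let the withdrawal response vary between patients with SD equal to s times the change SD. The change-score SE is multiplied by √(1 + s²), which is 1.00, 1.03 or 1.12 at s = 0, 0.25 or 0.5. The documents give no value for s.

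**Step 3: what moving the baseline draw to visit 1 could recover.** Write g² = s² × 2(1 − r), and let ρ be the repeatability of a patient's withdrawal response between visits 1 and 10. The adjusted variance is 1 + g² − r² with a screening baseline, and 1 + g² − (r + ρg²)²/(1 + g²) with a visit 1 baseline. At r = 0.5 and s = 0.5, g² = 0.25 and the screening value is 1.00. For visit 1:

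- ρ = 1: 1.25 − 0.75²/1.25 = 0.80, SE ratio 0.89
- ρ = 0.5: 1.25 − 0.625²/1.25 = 0.94, SE ratio 0.97
- ρ = 0: 1.25 − 0.5²/1.25 = 1.05, SE ratio 1.02

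The largest loss found is at r = 0.7, s = 0.5, ρ = 0. There g² = 0.15 and the ratio is √(0.724/0.660) = 1.05. With adjustment, the move breaks even at ρ = r(√(1 + g²) − 1)/g², which is 0.14 to 0.35 over r = 0.3 to 0.7 and s = 0.25 to 0.5.

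**Step 4: the two steps as power.** Simulation with 20,000 runs, 15 per arm, r = 0.5, true d = 1.0 in matched-state change SDs, and ρ = 1, the case most favourable to moving the draw:

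| s | Change score, screening | Adjusted, screening | Adjusted, visit 1 |
|---|---|---|---|
| 0 | 75% | 85% | 85% |
| 0.25 | 73% | 82% | 84% |
| 0.5 | 66% | 74% | 83% |

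False-positive rates were 4.7% to 5.3%. Adjustment adds 8 to 10 points in every row. The move adds 0, 2 or 9.

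**The case against.** A reader might infer that blood is shown to be mismatched on medication state while every other outcome is matched, and that the biomarker result is therefore biased. The documents do not support this.

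- The state at each draw is unstated. ON at screening is inferred from the cognition battery, and resumption of medication at visit 10 is not addressed.
- Motor assessments are all OFF in the visit plan (sections 3 and 8), but section 12.1 labels the final motor visit as on. Those passages contradict each other. Vital signs are taken on both ON and OFF visits.
- Nothing in the documents says that these three markers respond to PD medication. Keeping cognition off OFF days does not show that the plan regards serum markers as state-dependent.
- Both arms follow the same schedule, so a common shift cancels.

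All of this stands, and it limits the timing issue to possible noise. It is also fair to say that a change-score comparator is a reading of 12.2, not its text. The gain does not depend on that reading: adjustment also improves on visit 10 level alone (step 1).

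A draw at visit 1 has its own risk. Taken after the pre-stimulation video, venepuncture would fall inside the first acute motor comparison in section 11.1. Any such draw should come before that video.

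**Conclusion.** The point holds as a low-priority improvement. Its firm part is the analysis: 12.2 does not say how the baseline sample is used, and adjusting for it is expected to cut the SE by about 8% to 19% relative to a change score. That range rests on assumed correlations of 0.3 to 0.7 and on equal variances at the two draws.

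The medication-state part is weaker. Its size cannot be derived from the documents and may be zero. It costs precision and does not bias the between-arm effect. Within-arm change is a different matter: it could mix stimulation with time and a change of state, so it should not be read as a treatment effect. The value of moving the draw depends on an unknown repeatability. All of this concerns biomarkers under an exploratory aim in a pilot trial.

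**What to change.** **Main change, in 12.2, at no cost.** For each marker, on the scale chosen after the distribution checks already planned, estimate the between-arm difference in visit 10 level adjusted for baseline level. Report a 95% confidence interval with Cohen's d alongside, and state how d is computed. Label within-arm changes as descriptive. This uses only data already collected.

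**Cheap addition, in section 9.** Record time since last PD medication at each draw, since OFF is defined only as a minimum of 12 hours. State where in visit 10 the second draw falls.

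**Optional.** Consider taking the baseline draw at visit 1, before the pre-stimulation motor video, and only together with baseline adjustment. It adds no draw or visit. It comes after randomisation but before any stimulation, so it remains a valid covariate. A participant who leaves before visit 1 would have no visit 10 sample either. The costs are a slightly longer OFF visit and, if the withdrawal response is not repeatable, no gain or a loss of up to about 5% in adjusted SE. If adopted, update sections 3, 7.1 and 9 and the schedule.

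**Separately.** Reconcile the on label for the final motor visit in 12.1 with the OFF description of visit 10 in sections 3 and 8.
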